14. HEALTH ECONOMICS

14.1. Overall objectives for HE in the feasibility study

Although the standard economic evaluation framework has been developed in such a manner that it can be used to assess any use of scare resources to achieve improved health related quality of life improvements, interventions in mental health have specific idiosyncrasies which require additional attention. Whilst the evaluation of the full programme will meet NICE reference case standards and meet the CHEERS guidance in reporting outcomes, the feasibility study analysis will be limited to considering those elements which are considered most uncertain in the economic evaluation of mental health interventions. For example, we will not be considering the collection of secondary care costs in the feasibility study as we know complete records can be collected via Hospital Episode Statistics (HES). A consequence of this is that it is not really possible to draw conclusions about the overall economic argument from the feasibility trial, though we note this is not the underlying purpose of the feasibility study. In addition we will not use the feasibility study to determine the overall framework of analysis which will compare incremental Quality-Adjusted Life Years (QALYs) against incremental costs from both an NHS perspective but also from a wider societal perspective.

The feasibility study will assess the instruments we intend using for a) the measurements of Health Related Quality of Life (HRQoL) and therefore construction of QALYs and b) the measurements of resource use which are not captured by routine databases such as HES.

14.2. Feasibility of HRQoL Instrument

Whilst there is usually a preference for a completely generic measure of HRQoL such as the EQ-5D as suggested by NICE, there is sufficient evidence to suggest that the instrument is not particularly sensitive for use in all MH assessments. For this reason the CORE-6D instrument (derived from the CORE-OM) will be used. We will use the feasibility study to assess the completeness of response and the variation in self-reported HRQoL across patients and over time.

14.3. Feasibility of Resource Use Instruments

The feasibility study will also be used to assess the instruments used to capture self-reported resource use. From a medication/treatment perspective we will ask respondents to self-report use over the previous 3 months on the basis of providing a sufficient period of time in which to extrapolate over longer periods without incurring too much of a risk of recollection bias. The standard form is to identify the unit of resource use (medication, GP visit, residential rehabilitation centre stay) and quantify the number of units used. Much of this is standard in the economic evaluation of any technology. An important distinction from the cost-perspective is whether we can determine which are personal costs and which are costs to the NHS.

A key element in the assessment of the costs of MH interventions is the impact on the ability to work. There are no standardized or validated instruments for use in all economic evaluations in mental healthcare settings (23). In addition to the lack of standardized measure for use in MH, we also wish to explore the possibilities of distinguishing between costs due to unemployment, absenteeism and presenteeism. Ultimately they may have different costs associated with them but we also wish to explore the possibility of using these measures in the larger trial to understand transitions across these dimensions and we use the feasibility study to trial questions which have been drawn from a number of sources. In the event that these data are not well completed we will revert to a simpler set of workforce participation questions.

14.4. Modelling and Analysis perspective

Finally we will use the feasibility study to gain greater understanding of the mechanisms of the intervention and the population of patients. This is to better understand what the economic analysis of the full trial may look like and to pick up on any important drivers of costs or HRQoL which are not apparent from the wider literature. Any unanticipated outcomes from the study need to be assessed in terms of the likely impact on the economic evaluation.

15. OUTCOMES

The outcomes relate to intervention delivery, acceptability and feasibility of recruitment, follow-up and outcome data collection, as follows :

Intervention delivery and acceptability

- Number and proportion of therapists undergoing training and deemed competent.
- Therapy delivery by randomly allocated therapist, cross over of patients to therapists.
- Proportion of participants attending therapy, completing the required number of therapy sessions, number of early drop-outs from treatment, reasons for early drop outs, overall and by therapy type (BT, ACT, PIT).
- Availability and uptake of other treatments and services accessed by participants
- Proportion of participants taking up telephone "top up" contact at end of therapy.
- Proportion of participants and therapists delivering key intervention components, overall and by therapy type (BT, ACT, PIT) as recorded by the therapist
- Proportion of treatment sessions by method of delivery
- Participant and therapist fidelity to the intervention including fidelity to the self-harm modifications and to the individual psychological therapeutic approach overall and by therapy type (BT, ACT, PIT) as recorded by the researcher rated audio-recordings.
- Number and attendance of therapy specific supervision sessions.

Recruitment methods, uptake and follow-up

- Number of patients screened for eligibility, overall and by site
- Number of study cards given out and proportion completed, overall and by site
- Method of referral e.g. Emergency Department, self-harm team, clinical staff, general practice.
- Proportion of patients who complete the study card, who could be followed-up by the Researcher to assess eligibility and proportion of those found eligible for the study, overall and by site
- Proportion of patients that consent and are registered to the study out of those found eligible
- Reasons for non-participation, overall and by site
- Proportion of patients completing the study out of those registered, number of withdrawals from follow-up data collection, reasons for withdrawal, overall and by site
- Number of losses to follow-up and characteristics of participants lost to follow-up

Follow-up data collection

- Proportion of participants with available monthly self-reported repetition of self-harm data
- Proportion of participants with 6 month self-reported outcome data, proportion obtained through postal, online, telephone or face to face administration
- Proportion of participants with self-harm follow-up obtained through hospital records, text, and 6 month self-report
- Overall and item completion rates, and time spent on self-reported questionnaires.
- Proportion of participants reporting questionnaires as acceptable

Statistical outcomes

- Estimates and variability of self-reported outcomes at baseline and 6 months postrandomisation with 95% Confidence Intervals
 - Psychological global distress as measured by the CORE-OM.
 - Hopelessness as measured by the Beck Hopelessness Scale (BHS)
 - Depression as measured by the Patient Health Questionnaire- 9 (PHQ-9)

- Social connectedness as measured by the Social Connectedness Scale revised (SCS-R)
- Proportion of participants with reliable and clinically significant improvement (RCSI) defined as defined on the CORE-OM (16, 24, 25) as: change in CORE-OM of 5 or more points (reliable) and movement from the clinical range (≥10/40) to the non-clinical range (<10/40) (clinically significant).
- Clustering effect (ICC) of the CORE-OM by therapist and by therapy modality

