11.3. Therapist identification

The intervention will be delivered by health professionals (mental health nurses, psychologists, OTs or psychiatrists, counsellors) who have either prior experience of work with people who self-harm and managing risk, or who are trained in one of the three therapies. Some prior experience of delivering any form of recognised therapy is desirable but not essential. Good interpersonal skills are essential as judged by being able to form strong working alliances with clients/users.

Potential therapists will be identified at each site following discussion with the relevant service managers. All therapists will have a recognised mental health professional background (eg. Nursing, occupational therapy, clinical psychology, psychiatry, CBT therapist, counsellor). We aim to recruit two therapists for each type of therapy at each site, with at least two of the three therapies made available at each site.

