12.6. Fidelity assessment instruments

Fidelity assessment of assessment and therapy sessions in the intervention arm will be made using a selection of items from the therapy-specific scales described below for fidelity to the individual psychological therapeutic approach, supplemented with additional items to assesses adaptations for self-harm.

For comparability across therapies, a single fidelity measure that captures common features across therapies will be scored, based upon responses in each of these therapy-specific measures.

BT/CBT: The Cognitive Therapy Scale (Revised) (CTS-R).

The Cognitive Therapy Scale (Revised) (CTS-R) is a widely used measure of competence for Cognitive Behavioural Therapies (22). It assesses the competence with which specific behavioural and cognitive techniques are used in therapy along with an assessment of more general therapeutic skills (e.g., interpersonal effectiveness, collaboration, pacing).

PIT: The Sheffield Psychotherapy Rating Scale

The Sheffield Psychotherapy Rating Scale is a 59 item scale using 7-point rating scales. It assesses the therapist's adherence to manuals for cognitive and interpersonal therapy. Trained raters rating the extent to which the therapist engages in each of the required behaviours (Shapiro, D and Startup, M., (2010) *Measuring Therapist Adherence in Exploratory Psychotherapy*, Psychotherapy Research, 2:3, 193-203). This measure has been validated for people with depression.

ACT: ACT Fidelity measure (ACT-FM)

The ACT Fidelity Measure (ACT-FM) records the fidelity of therapist behaviours the ACT treatment model. It includes 25 items, grouped into sub-domains recording pre-scribed and pro-scribed therapist behaviours in relation to ACT. It was developed recently via an expert Delphi study and field test with practicing clinicians. The measure shows acceptable inter-rater reliability and is rated as practicable by raters.

Therapist completed adherence checklist

An adherence checklist will be designed for use in the study, to be completed by the treating therapist following each intervention session.

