17. STATISTICAL CONSIDERATIONS

17.1. Sample size:

We plan to recruit 30 participants to provide sufficient data to assess progression criteria to inform the decision to move to a definitive randomised Phase III evaluation (WP4). As this study is designed to determine the feasibility of a confirmatory trial and not to assess proof of concept or evaluate effectiveness, formal power calculations are not appropriate

Progression criteria will assess recruitment, follow-up, delivery and acceptability of the intervention using a traffic light system (Table 2). With 30 participants, the 95% CI around our green (go) criteria will exclude values in the red zone, relating to our stopping criteria. Therefore, with 30 patients, should we meet the go criteria we can be sufficiently confident that follow-up, delivery and acceptability will not fall to unacceptable levels as defined by the red (stop) criteria.

Recruitment of 30 participants will take place over four months in four centres, with approximately two to three participants recruited per month per center. With at least two therapists per center, this corresponds to one to two new participants a month per therapist, in line with recruitment and capacity requirements for the planned definitive trial (WP4).

Table 2 Feasibility study progression criteria

	Red	Amber	Green
			(95% CI)
Recruitment : Average no. patients	<4	4-7	>7
recruited / month			

Follow-up: % patients completing	<60%	60-75%	>75%
6m primary outcome			(95% Cl: 59.5%, 90.5%)
Delivery: % therapist delivering	<60%	60-80%	>80%
key intervention components			(95% Cl: 65.7%, 94.3%)
(overall and by each therapy)			
Acceptability: % participants	<50%	50-70%	>70%
attending 1st session			(95% CI: 53.6%, 86.4%)

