17.3. Analysis Populations

All analyses and data summaries will be conducted on the intention-to-treat (ITT) population which is defined as all participants registered regardless of non-compliance with the protocol or withdrawal from the study.

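### The Delivery progression criterion has no consistent unit or denominator, and its printed interval fits only a count of 30 participants

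*Protocol*

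**What the plan says.** Four places in the protocol bear on how Delivery is counted.

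- **Section 15, Outcomes:** "Proportion of participants and therapists delivering key intervention components, overall and by therapy type (BT, ACT, PIT) as recorded by the therapist". Two units appear in one outcome.
- **Section 17.1, Table 2:** the row begins "Delivery: % therapist delivering" and is to be judged overall and for each therapy. Red is below 60%, Amber 60% to 80%, Green above 80%. The Green cell carries "95% Cl: 65.7%, 94.3"%. The row beneath, "Acceptability: % participants" attending the first session, has cut-offs of 50% and 70%.
- **Section 17.3, Analysis Populations,** sets a single rule: "All analyses and data summaries will be conducted on the intention-to-treat (ITT) population which is defined as all participants registered regardless of non-compliance". No exception is made for delivery or fidelity.
- **Section 12.6, Fidelity assessment instruments:** the therapist's adherence checklist is "to be completed by the treating therapist following each intervention session". A participant who attends no session therefore has no checklist.

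Section 17.1 ties the sample size to these criteria: "We plan to recruit 30 participants to provide sufficient data to assess progression criteria". It adds that, with 30 participants, the interval around each Green criterion excludes the Red zone.

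**The concern.** Delivery is one of four progression criteria for the definitive trial. Its natural purpose is to show whether trained therapists deliver the adapted therapy when they see a patient. The label counts therapists, the interval counts 30 participants, and the population rule keeps in the denominator people who can produce no delivery record.

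The choice can change the traffic-light result. On a count of all registered participants, non-attendance can enter twice: once in the Acceptability row, and again in Delivery against stricter cut-offs. On a count of therapists, the number of units is well below 30, and the assurance in section 17.1 that the interval stays clear of Red may not hold. If the unit is left open until the data are in, the colour of the row could depend on a choice made after seeing them.

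**Working it through.** **Inputs.** 30 participants and the Table 2 cut-offs (section 17.1). Four sites (section 8). Therapists: at least two per centre in section 17.1 gives 4 × 2 = 8. Section 11.3 plans a pair of therapists per therapy and two or three therapies per site, which gives 4 × 2 × 2 = 16 or 4 × 3 × 2 = 24. Attendance rates are assumptions; the protocol gives none.

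**1. Reproduce the printed intervals.** Wald: p ± 1.96 × √(p(1 − p)/n), with n = 30.

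| Row | p | Computed | Printed |
|---|---|---|---|
| Follow-up | 75% | 59.5% to 90.5% | 59.5% to 90.5% |
| Delivery | 80% | 65.7% to 94.3% | 65.7% to 94.3% |
| Acceptability | 70% | 53.6% to 86.4% | 53.6% to 86.4% |

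For Delivery at n = 30, Clopper-Pearson gives 61.4% to 92.3% and Wilson 62.7% to 90.5%. Wald at n = 29 gives 65.4% to 94.6% and at n = 31 gives 65.9% to 94.1%. Of the variants tried, only Wald with n = 30 matches.

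**2. Participant count, all 30 registered, non-attenders scored as not delivered, perfect delivery at every session held.** The highest possible Delivery is then (number attending)/30.

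| Attending | Acceptability | Highest possible Delivery |
|---|---|---|
| 21 | 70.0%, Amber | 70.0%, Amber |
| 22 | 73.3%, Green | 73.3%, Amber |
| 23 | 76.7%, Green | 76.7%, Amber |
| 24 | 80.0%, Green | 80.0%, Amber |
| 25 | 83.3%, Green | 83.3%, Green |

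Binomial probability of 22 to 24 attending out of 30, by assumed true attendance:

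| True attendance | 70% | 75% | 80% | 85% | 90% |
|---|---|---|---|---|---|
| P(22 to 24) | 35.5% | 47.1% | 44.4% | 26.2% | 7.1% |

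With attenders as the denominator the conflict goes. Green needs 18 of 22 (81.8%), 19 of 23 (82.6%) or 20 of 24 (83.3%).

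**3. Therapist count.** A therapist with m participants has at least one attender with probability 1 − (1 − a)^m. Assume a = 70%, independent attendance, and 30 participants spread as evenly as possible. A therapist with no attender is counted as not delivering.

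- 8 therapists (six with 4, two with 3): (6 × 0.9919 + 2 × 0.973)/8 = 98.7%.
- 16 therapists (fourteen with 2, two with 1): (14 × 0.91 + 2 × 0.70)/16 = 88.4%; the chance that the ceiling exceeds 80% is 90%.
- 24 therapists (six with 2, eighteen with 1): (6 × 0.91 + 18 × 0.70)/24 = 75.2%; the chance that it exceeds 80% is 25%.

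**4. Wald interval at 80% for other denominators.**

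| n | Interval | Lower limit against Red (<60%) |
|---|---|---|
| 8 therapists | 52.3% to 107.7% (passes 100%) | inside Red |
| 16 therapists | 60.4% to 99.6% | just clear |
| 24 therapists | 64.0% to 96.0% | clear |
| 21 attenders | 62.9% to 97.1% | clear |

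**The case against.** The strongest reply is that nothing in the protocol says a non-attender is scored as not delivered. Section 17.3 says who is included, not how an absent record is scored. It also cannot literally set every denominator, because section 15 has outcomes counted over therapists, over sessions and over people screened before registration. Where section 15 wants registered participants as the base it can say so, as it does for study completion. The Table 2 label counts therapists, and the n = 30 intervals may be no more than planning illustrations. Section 17.3.2 says the methods for measuring adherence and fidelity are still to be agreed, and section 17.2 promises a full analysis plan.

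Most of this stands, and it limits the finding. A reader might infer that the plan does count non-attenders as failures, or that the Delivery and Acceptability rows cannot both be Green. The documents support neither. The first is an inference, and 25 of 30 attending allows Green on both rows. The 47.1% belongs to one assumed attendance rate and falls to 7.1% at 90%. On a therapist count with 8 therapists the attendance effect almost disappears, and with 16 it is modest. Amber is not a stop.

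The reply does not remove the mismatch. The protocol itself fixes the label, the population rule, the cut-offs and the interval, and they do not fit together. If therapists are the unit, the printed interval is wrong. If registered participants are the unit, the label is wrong and the attendance cap is open. Leaving scoring detail to an analysis plan does not repair a criterion whose published parts disagree.

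**Conclusion.** The point holds as an inconsistency of unit and denominator in a progression criterion. On a count of all 30 registered, with non-attenders scored as not delivered, 22 to 24 attending gives Green Acceptability and at best Amber Delivery, however well therapists perform. On a therapist count, attendance matters little with 8 therapists (expected ceiling 98.7%), somewhat with 16 (88.4%) and materially with 24 (75.2%). The n = 30 interval is wrong in each case, and with 8 therapists the correct lower limit of 52.3% lies in Red, against the assurance in section 17.1.

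The attendance figures rest on assumed rates, independence and, for therapists, an even spread. The interval results rest only on the Wald formula that reproduces Table 2 and on therapist numbers derived from sections 8, 11.3 and 17.1. The matter should be settled before data are seen, because the choice can change the colour of the row.

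**What to change.** - In Table 2 and section 15, state one unit for Delivery. Either count therapists who held at least one trial session, or count participants who attended at least session 1.
- Write this as an explicit exception to section 17.3, and report how many therapists or participants are left out.
- Judge attendance only in the Acceptability row.
- Restate the Delivery interval for the chosen denominator, for example 62.9% to 97.1% at 80% of 21 attenders, or 60.4% to 99.6% with 16 therapists.
- Limit the section 17.1 statement that the interval excludes Red to the cases where it does.

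The cost is wording in the protocol and matching text in the analysis plan. No new data or participants are needed. The downside is a wider stated interval for Delivery.

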16. QUALITATIVE INTERVIEW STUDY

The feasibility will include an embedded qualitative interview study to explore the acceptability of the approach from a service user perspective and to gain insights into how service users feel the therapy may work in practice This qualitative study will complement a related interview and observational study with the therapists and other key stakeholders to explore key implementation issues from a service perspective (approved by the University of Leeds School of Medicine Ethics Committee). Findings from both these studies will be used to refine the therapist training and finalise recruitment and follow-up procedures for the definitive trial. The findings will also be used to finalise a logic model that can guide the process evaluation of the definitive trial.

16.1. Sample identification:

Participants will be asked at time of enrolment to the feasibility study if they are willing to be approached to take part in this qualitative study. A sample of participants who consent (n=18) will then be approached by a study researcher to take part in this study.

16.2. Procedure:

Participants

Consenting participants will be interviewed at the end of therapy to explore their experiences of the therapy and the perceived impact on their social and psychological well-being. Participants will be asked about the appropriateness and acceptability of the measures and procedures for recruitment and follow-up. In addition, the effects of the COVID19 pandemic and the lockdown will be explored. A topic guide will be used to guide the interview. Interviews can be held via telephone or video call.

16.3. Data collection and storage:

Interviews will be audio recorded*, following agreement from the interviewee, using a digital audio recording device and will be professionally transcribed by University of Leeds approved GDPR compliant transcribers. During transcription, any potentially identifying information that may be contained in the interview discussions will be anonymised or removed. Only the research team and the transcriber will listen to the interview audio files. Audio files will be securely transferred in encrypted format, and securely stored at LIHS, accessible to only those members of the study team requiring such access. Field notes from observations and interviews will also be stored at LIHS. Where interviews are held via video calling only audio will be recorded.

16.4. Analysis:

Data from the interviews will be analysed for content thematically using a framework approach. The framework will be developed from the intervention development work in earlier stages of the programme of work. Intervention development also involves interviewing therapists involved in the feasibility study; this element of the project is dealt with in a separate protocol. The output from this analysis will be the refined training materials and finalised procedures for the definitive trial.

A second, theory driven analysis will explore participants' responses to identify how their experiences resonate with, and help to refine, our initial theories as to how this intervention might work to enact change. For example, a programme theory from our initial logic model is "identifying an individual's values through understanding the function of self-harm for them will facilitate engagement with therapy as clients feel respected". Analysis will explore where participant experience confirms or refutes initial theories and identify potential adjustments to, or caveats on, programme theories. The output from this analysis will be a logic model that can be used to guide the process analysis of the definitive trial.

